5.2.3.2 Per-Protocol Analysis Set for CMI (PPAS-CMI)

Subset of PPAS excluding participants who provided all post-dose CMI samples outside the proper time window or no post-dose CMI sample was drawn.

5.2.4 Other Analysis Sets

Randomized subjects

A randomized subject is a subject for whom a randomized group has been allocated by IRT.

Subjects with data in CRF

Subjects with data in CRF are subjects for whom data were recorded at a visit (except screening).

5.2.5 Populations Used in Analyses

The primary immunogenicity analyses, the secondary immunogenicity analyses, and the exploratory immunogenicity analyses (excluding CMI analyses) will be performed on the PPAS-IAS, and will be confirmed on the FAS.

The primary safety analysis will be performed on the SafAS.

The secondary efficacy analyses will be performed on FAS and PPAS-IAS.

The CMI analyses in the exploratory objective will be performed on PPAS-CMI, and will be confirmed on the FAS.

5.3 Handling of Missing Data and Outliers

5.3.1 Safety

Generally, no replacement will be done. However, imputations may be done for a limited number of scenarios, some of which are described in this section.

5.3.1.1 Immediate

Unsolicited systemic AEs with a missing response to the “Immediate” field will be assumed to have occurred within the 30-minute surveillance period.

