2.3.3 Overall Benefit-Risk Conclusion

Considering the significant medical need, scale of the pandemic, urgent requirement for measures to address the pandemic, together with actions taken to minimize risk to participants enrolled in the study, there is no unreasonable and significant risk of illness or injury for the participants.

3 Objectives and Endpoints

The study objectives and the corresponding endpoints are described in [Table 3.1](#).

Table 3.1: Objectives and endpoints

Objectives	Endpoints
Primary	
Immunogenicity To describe the neutralizing antibody profile at D01, D22, and D36 of each study intervention group.	Immunogenicity Neutralizing antibody titers will be measured with the neutralization assay. 
• Antibody titer at D01, D22, and D36• Fold-rise (fold-rise in serum antibody neutralization titer post-vaccination relative to D01) at D22, and D36• 2-fold and 4-fold rise in serum neutralization titer (post/pre) relative to D01 at D22, and D36• Occurrence of neutralizing antibody seroconversion, defined as baseline values below lower limit of quantification (LLOQ) with detectable neutralization titer above assay LLOQ at D22 and D36
Safety To describe the safety profile of all participants in each age group and each study intervention group up to 12 months post-last dose.	Safety 
• Presence of unsolicited systemic AEs reported in the 30 minutes after each injection• Presence of solicited (pre-listed in the participant's diary card and Case Report Form [CRF]) injection site reactions and systemic reactions occurring up to 7 days after each injection• Presence of unsolicited AEs reported up to 21 days after each injection• Presence of medically attended adverse events (MAAEs) throughout the study• Presence of serious adverse events (SAEs) and adverse events of special interest (AESIs) throughout the study• Presence of out-of-range biological test results up to 7 days post-last dose (ie, up to D09 for Cohort 1 and up to D30 for Cohort 2)

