All noxious and unintended responses to a study intervention related to any dose should be considered adverse reactions (AR).

(The phrase “responses to a study intervention” means that a causal relationship between a study intervention and an AE is at least a reasonable possibility)

Immediate Event/Reaction:

Immediate events are recorded to capture medically relevant unsolicited systemic AEs (including those related to the study intervention administered) that occur within the first 30 minutes after vaccination.

Medically Attended AE (MAAE)

An MAAE is a new onset or a worsening of a condition that prompts the participant to seek unplanned medical advice at a physician’s office or Emergency Department. Physician contact made over the phone or by e-mail will be considered a physician office visit for the purpose of MAAE collection. This includes medical advice seeking during the study visit or routine medical care. This definition excludes pediatric check-ups, follow-up visits of chronic conditions with an onset prior to entry in the study, and solicited reactions.

Injection Site Reaction/Administration Site Reactions:

An injection/administration site reaction is an AR at and around the injection/administration site. Injection/administration site reactions are commonly inflammatory reactions. They are considered to be related to the study intervention administered.

Systemic AE/AR:

Systemic AEs are all AEs that are not injection or administration site reactions. They should therefore include systemic manifestations such as headache, fever, as well as localized or topical manifestations that are not associated with the vaccination or administration site (eg, erythema that is localized but that is not occurring at the injection site).

Systemic AEs assessed as related to study intervention are referred as systemic ARs. Solicited systemic reactions occurring during the specified collection period are always considered related to the study vaccine even if there is evidence or alternative etiology.

Adverse Event of Special Interest (AESI):

An adverse event of special interest (serious or non-serious) is one of scientific and medical concern specific to the Sponsor’s study intervention or program, for which ongoing monitoring

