4.4.1.2.4 Time of Onset

Time of onset is derived from the start date of the unsolicited AE provided in the clinical database and the date of last vaccination as described in [Section 4.4.1.2.2](#):

Time of Onset = start date of the unsolicited AE – date of last vaccination before the unsolicited AE + 1

The time of onset should be considered as missing only if one or both of the dates are missing or partially missing.

The unsolicited AEs will be analyzed “Within 21 days”, which corresponds to AEs with a time of onset between 1 and 22 days or missing.

An AE with missing time of onset will be considered to have occurred just after the vaccination indicated by the visit number in “Appeared after visit” or similar field, so will be included in these tables.

Time of onset will be displayed as follows:

- D01-D04
- D05-D08
- D09-D15
- D16 or later
- Missing

Note: To further clarify the analysis:

- Any unsolicited AEs reported up to the entire study period (SAEs, MAAEs, AESIs) with time of onset > 22 days after each injection will not be presented in tables of unsolicited AEs within 21 days but only in tables of SAEs, MAAEs, AESIs and NOCMCs.

- Any unsolicited AEs reported up to 21 days with time of onset between 1 and 22 days or missing after each injection will be presented in the tables of unsolicited AEs within 21 days.
- Any unsolicited AEs reported up to 21 days with time of onset > 22 days after each injection will not be presented in any tables but listed separately.
- Any unsolicited AEs with null (0) or negative time of onset will be excluded from the above tables and listed separately

Safety analysis will include only those unsolicited AEs with time of onset before a participant received a non-study authorized/approved COVID-19 vaccine if applicable. Events with time of onset on or after the date of receiving a non-study authorized/approved COVID-19 vaccine will be listed separately.

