5.1.1.2 Statistical Methods for Primary Safety Objective

Safety results will be described for each age and vaccine group. The homogeneity of pooled groups will be assessed on the main parameters. The main parameters will be described with 95% CI.

Safety analyses will be performed based on safety analysis set including safety data collected before the date of receiving an authorized/approved COVID-19 vaccine. Safety data collected on or after the day of receiving an authorized/approved COVID-19 vaccine will be listed separately.

Solicited Reactions

Number and percentage of subjects with:

- Presence of solicited injection site reactions and systemic reactions occurring up to 7 days after injection
- Each solicited reaction according to time of onset, maximum intensity, and number of days of occurrence over the solicited period

Unsolicited Events and Reactions

Number and percentage of subjects with:

- Any unsolicited immediate systemic event in the 30 minutes after injection
- Any unsolicited event and reaction (using the current MedDRA version) 21 days after injection
- Any unsolicited event/reaction according to time of onset, maximum intensity, and duration

SAEs

Number and percentage of subjects with:

- any SAE within 21 days after injection and during the 6 months and 12 months follow-up periods according to SOC and PT, seriousness and outcome

AEs of special interest

- Number and percentage of subjects with any/each AESI within 21 days after injection and during the 6 month and 12 months follow-up periods will be presented according to SOC and PT, seriousness and outcome.

MAAE

- Presence of medically attended adverse events (MAAEs) throughout the study

Laboratory tests

- Presence of out-of-range biological test results up to 7 days post-last dose (ie, up to D09 for Cohort 1 and up to D30 for Cohort 2)

The following analyses will be performed for laboratory tests in addition to the summary of out of range tests above:

- Biological test results and toxicity grade by visit,

- Summary of toxicity grade shift from baseline,

For descriptive purposes, the statistics presented on [Table 5.1](#) will be produced.

In addition to analyses by each intervention group, aggregated groups will be used to perform complementary assessments for above parameters, including:

1. aggregated vaccine group, ie, all vaccine arms pooled
2. aggregated placebo group, ie, two placebo arms pooled

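### SAP 5.3.1.1 counts an unsolicited systemic AE with a blank Immediate field as a 30-minute event even when its recorded start date puts onset on days 2 to 22

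*SAP*

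**What the plan says.** - **Imputation rule, SAP 5.3.1.1.** An unsolicited systemic AE whose Immediate response is missing "will be assumed to have occurred within the 30-minute surveillance period". This is the whole rule; it does not mention the start date.
- **Endpoint, Protocol Table 3.1.** The first primary safety endpoint listed is "Presence of unsolicited systemic AEs reported in the 30 minutes after each injection". SAP 5.1.1.2 reports it as the number and percentage of participants with "Any unsolicited immediate systemic event in the 30 minutes after injection".
- **Definition, Protocol 10.3.1.** Immediate events are medically relevant unsolicited systemic AEs "that occur within the first 30 minutes after vaccination".
- **Onset, SAP 4.4.1.2.4.** "Time of onset is derived from the start date of the unsolicited AE provided in the clinical database". The formula begins "Time of Onset = start date of the unsolicited AE", then subtracts the date of the last vaccination and adds 1, so the vaccination day is day 1. Onset is displayed as D01-D04, D05-D08, D09-D15, D16 or later, or missing.
- **Late events, SAP 4.4.1.2.4.** SAEs, MAAEs and AESIs with onset beyond day 22 "will not be presented in tables of unsolicited AEs within 21 days but only in tables of SAEs, MAAEs, AESIs and NOCMCs". Unsolicited AEs collected only for the 21-day period, "with time of onset > 22 days after each injection will not be presented in any tables but listed separately".

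**The concern.** A missing-data rule should fill in what is unknown. When the start date is complete and falls after the vaccination day, it is already known that the event did not begin within 30 minutes of that injection. The rule in 5.3.1.1 nevertheless assigns it to that window. The same record can then be immediate in one output and fall in a later onset category in another.

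The study is descriptive (Protocol 9.1), so no test, type I error rate or power is affected. What is at stake is the safety description itself. The percentages and intervals by group are the primary result, and most age-by-arm groups have 10 or 20 participants, so a single misclassified record is visible.

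**Working it through.** The plan states no rate of immediate events and no rate of blank fields, so there is no figure of its own to reproduce.

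**Step 1. The contradiction, by example.** Take an injection on Day 1, an AE with a complete start date on Day 15, and a blank Immediate field.
- SAP 4.4.1.2.4: time of onset = 15 − 1 + 1 = 15, displayed under D09-D15.
- SAP 5.3.1.1: within 30 minutes of injection.
- Protocol 10.3.1: not an immediate event.

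The same conflict arises for every onset from day 2 to day 22. It does not arise on day 1, where dates cannot resolve minutes, or when onset is missing.

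**Step 2. Direction.** The rule turns blanks into yes and never turns yes into no. Any error it makes can only raise the count.

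**Step 3. Effect of one misfiled participant.** Group sizes are from Protocol Table 4.2. Intervals are Clopper-Pearson, as in Protocol 9.4.2.2. For 0/n the upper limit is 1 − 0.025^(1/n); for 1/n the lower limit is 1 − 0.975^(1/n), and the upper limit is the 0.975 quantile of Beta(2, n − 1). The comparison assumes no true immediate events in the group.

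| Group size | 0 events: % (95% CI) | 1 event: % (95% CI) |
|---|---|---|
| 10 | 0 (0 to 30.8) | 10.0 (0.3 to 44.5) |
| 20 | 0 (0 to 16.8) | 5.0 (0.1 to 24.9) |
| 30 | 0 (0 to 11.6) | 3.3 (0.1 to 17.2) |
| 60 | 0 (0 to 6.0) | 1.7 (0.04 to 8.9) |
| 90 (both ages, Cohort 2 AS03 arm) | 0 (0 to 4.0) | 1.1 (0.03 to 6.0) |

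**Step 4. How many there might be.** This rests on assumptions. Let *a* be the share of participants with an unsolicited systemic AE of onset day 2 to 22 (one each), and *m* the chance that its Immediate field is still blank at lock. The added rate is *a* × *m*, and the chance of at least one false case in n participants is 1 − (1 − *am*)^n.
- Over *a* = 10% to 40% and *m* = 0 to 10%, the added rate runs from 0 to 4.0 percentage points, or 0 to 440 × 0.04 = 17.6 expected false cases in 440.
- At *a* = 20% and *m* = 2%, *am* = 0.4%, giving 440 × 0.004 = 1.76 expected cases. The chance of at least one is 7.7% in a group of 20, 30% in 90 and 83% in 440.
- At *m* = 0 the effect is nil.

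**Step 5. After the change.** If the imputation applies only to onset on day 1 or missing, an AE with onset on day 2 or later adds nothing, and each right-hand entry in the table returns to the left-hand one.

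**The case against.** The best defence is that this is a deliberate worst-case convention, used consistently. SAP 5.3.1.2 counts missing causality as related, and 4.4.1.2.4 places an AE with missing onset just after the vaccination. Such a rule may overstate risk but cannot hide an acute event. That is sound when onset is on the vaccination day or unknown. With a known later date there is no uncertainty left to be conservative about.

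A second defence is that few blanks should survive. The 30-minute surveillance is collected in the CRF (Protocol Tables 1.1 and 1.2) and documented in source (8.4.1). Data are checked and verified against source (10.1.7), and a data review precedes lock (SAP 5.6). This stands as a reason to expect a small effect. It does not repair the rule for the blanks that remain.

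Three stronger readings are tempting and are not supported:
- **That an SAE or MAAE at month 6 would be counted as immediate.** SAP 4.4.1.2.4 confines SAEs, MAAEs and AESIs with onset beyond day 22 to their own tables and sends other such AEs to listings. The two sections do not refer to each other, so the SAP should make the precedence explicit, but the firm case is days 2 to 22.
- **That the endpoint is inflated.** This needs blanks on records with a known later onset. The documents give no frequency. Nor do they show whether the field is mandatory or whether sites tend to skip it for later events.
- **That the error distorts the assessment of anaphylaxis or triggers a safety pause.** Anaphylactic reactions are captured separately as an AESI (Protocol 8.4.6, SAP 4.4.1.4.7). Immediate reactions are reviewed at the ESDR, but none of the criteria in Protocol 8.4 is a count of immediate events, and nothing says that the SAP's imputations apply there.

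**Conclusion.** The point holds for AEs with a derived time of onset on days 2 to 22. For these, SAP 5.3.1.1 as written overrides a recorded date and conflicts with SAP 4.4.1.2.4 and Protocol 10.3.1, on a primary safety endpoint. The text and the direction of any error are certain; the size is not. Per misfiled participant it is 10 percentage points in a group of 10, 5 in a group of 20 and 1.7 in a group of 60, assuming that participant has no true immediate event. The number of such participants depends on a blank-field rate that the documents do not give and that may be zero. It should be corrected because the correction is nearly free, not because harm to the results has been shown.

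**What to change.** Replace SAP 5.3.1.1 with:

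*An unsolicited systemic AE with a missing Immediate response is treated as immediate only if its derived time of onset (Section 4.4.1.2.4, with last vaccination assigned per Section 4.4.1.2.3) is day 1 or missing. If the time of onset is day 2 or later, it is treated as not immediate. The number of imputed events is reported by group.*

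Two details make this work.
- The condition should rest on derived onset, not on whether the start date matches any injection date. In Cohort 2, an AE starting on the day of the second injection is on one injection date and after another. Section 4.4.1.2.3 already settles which vaccination applies, using the visit field.
- Missing onset should mean missing as defined in 4.4.1.2.4. Section 5.3.1.5 also sets onset to missing when only the stop date is absent, which would bring an AE with a known later start back into the imputation. The two sections should be aligned.

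The cost is a short SAP edit, one condition in the derivation program and one reported count. Worst-case handling stays wherever the date leaves doubt. A partial database lock has already taken place, so completed interim outputs should be checked for affected records and the new rule used in later analyses.

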5.3.1.2 Causality

By convention, all events reported at the injection site (either solicited or unsolicited) will be considered as related to the administered product and then referred to as reactions. In a same way, all solicited systemic events pre-listed in the CRF are also considered as related to vaccination and will be considered as reactions. Missing causality for unsolicited non-serious AEs and SAEs will be considered at the time of analysis as related to vaccination.

5.3.1.3 Measurements

Partially missing temperatures will be handled as described in [Section 4.4.1.1.1](#).

5.3.1.4 Intensity

For solicited reactions, missing intensities will be handled as described in [Section 4.4.1.1.1](#). For unsolicited non-serious AEs, missing intensities will remain missing and will not be imputed.

5.3.1.5 Start Date and Stop Date

Missing or partially missing start dates for unsolicited AEs will remain missing and not be imputed. If either the start or stop date is missing or partially missing, the time of onset will be considered to be missing. Nevertheless, unsolicited AEs with missing time of onset will be included in analyses according to the visit collected.

Missing or partially missing stop dates for AEs (solicited reactions and unsolicited AEs) will remain missing and not be imputed.

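### SAP 5.3.1.5 makes AE onset depend on the stop date, contradicting SAP 4.4.1.2.4; if followed, late SAEs, AESIs and MAAEs with no stop date enter the 21-day tables

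*SAP*

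**What the plan says.** SAP 4.4.1.2.4 defines the variable: "Time of onset is derived from the start date of the unsolicited AE provided in the clinical database and the date of last vaccination". The formula is start date minus date of last vaccination, plus 1. On missing values the section says: "The time of onset should be considered as missing only if one or both of the dates are missing or partially missing". The two dates meant are those in the formula.

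The same section defines the 'Within 21 days' analysis, "which corresponds to AEs with a time of onset between 1 and 22 days or missing". It then explains what happens to the missing ones: "An AE with missing time of onset will be considered to have occurred just after the vaccination indicated by the visit number", and they are included in these tables. For SAEs, MAAEs and AESIs with onset beyond 22 days it gives the opposite instruction: they "will not be presented in tables of unsolicited AEs within 21 days but only in tables of SAEs, MAAEs, AESIs and NOCMCs".

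SAP 5.3.1.5, on missing data, has a different rule for the same variable: "If either the start or stop date is missing or partially missing, the time of onset will be considered to be missing". It continues: "Nevertheless, unsolicited AEs with missing time of onset will be included in analyses according to the visit collected". On stop dates it says: "Missing or partially missing stop dates for AEs (solicited reactions and unsolicited AEs) will remain missing and not be imputed".

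The stop date has its proper place in SAP 4.4.1.2.5, where duration is derived from the start and end dates and is missing if either is missing.

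**The concern.** The stop date is not an input to time of onset, so a missing stop date gives no reason to discard an onset that can be computed. SAP 5.3.1.5 discards it all the same, and the 21-day filter accepts every missing onset.

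Unsolicited AEs up to 21 days after each injection are a primary safety endpoint (Protocol Table 3.1). SAEs, AESIs and MAAEs are collected for the whole study (Protocol 8.4.1). New-onset chronic medical conditions, one class of AESI, are by definition expected to last at least 3 months, so they are among the events most likely to have no stop date. At stake is whether the 21-day table describes a 21-day window for these events.

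The same sentence has two further effects:

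- **Onset display.** An AE that started on day 10 and is still ongoing moves from the D09-D15 row to the Missing row.
- **Cut at non-study vaccination.** SAP 4.4.1, 4.4.1.2.4, 4.4.1.2.6, 4.4.1.4.7 and 4.4.1.4.8 keep only events with onset before a non-study COVID-19 vaccine. SAP 4.4.1.2.2 and 4.4.1.2.5 classify AEs by onset relative to that date even when the stop date falls on or after it. With a blank stop date, 5.3.1.5 removes the derived onset that these rules need.

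**Working it through.** The plan states no figure on this point, so there is none to reproduce. The check applies both rules to the same events.

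**Inputs**
- Onset = start date − last vaccination date + 1 (SAP 4.4.1.2.4).
- Rule A (SAP 4.4.1.2.4): missing only if the start date or vaccination date is missing.
- Rule B (SAP 5.3.1.5): missing if the start date or stop date is missing.
- Filter for the 21-day tables: onset 1 to 22, or missing (SAP 4.4.1.2.4).
- Vaccination on day 1; stop dates not imputed (SAP 5.3.1.5). A blank stop date for an ongoing AE is assumed.

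**Results**

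| AE | Onset, rule A | In 21-day table? | Onset, rule B | In 21-day table? |
|---|---|---|---|---|
| Start D10, stop D15 | 10 | yes | 10 | yes |
| Start D10, ongoing | 10 | yes | missing | yes, in Missing row |
| Start D100, stop D120 | 100 | no | 100 | no |
| Start D100, ongoing | 100 | no | missing | yes |
| Start D300, ongoing | 300 | no | missing | yes |

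Under rule B, two events with the same known start on day 100 are treated differently only because one has resolved. Under rule A both stay out.

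**Which events can be late.** Non-serious unsolicited AEs that are neither AESI nor MAAE are collected only to day 22 after each vaccination (Protocol 8.4.1). The misfiling is therefore limited to SAEs, AESIs and MAAEs. Their exposure is long: follow-up after the last injection spans 366 days counting the injection day (D01 to D366 in Cohort 1, D22 to D387 in Cohort 2), and (366 − 22)/366 = 344/366 = 94% of it lies after day 22.

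**Illustrative size.** Assume 1% to 5% of participants have a late event of this kind with a blank stop date.
- Whole study: 440 × 0.01 = 4.4; 440 × 0.05 = 22.
- An AS03 arm in Cohort 2 (60 + 30 = 90): 90 × 0.01 = 0.9; 90 × 0.05 = 4.5.
- Chance of at least one in a group of n is 1 − (1 − p)^n. For p = 1%, 2% and 5% this is 18%, 33% and 64% when n = 20, and 10%, 18% and 40% when n = 10.

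**Effect of one misfiled event on a proportion** (Clopper-Pearson, the SAP's method), if the participant has no other 21-day AE:
- n = 20: from 0/20 (95% CI 0 to 16.8%) to 1/20 = 5.0% (0.1 to 24.9%).
- n = 10: from 0/10 (0 to 30.8%) to 1/10 = 10.0% (0.3 to 44.5%).

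**The case against.** The best defence is that 5.3.1.5 contains a drafting slip and the derivation section will govern. SAP 4.4.1.2.4 gives the formula, limits missing onset to its own two dates, and expressly bars late SAEs, MAAEs and AESIs from the 21-day tables. SAP 4.4.1.2.5 shows where the stop date belongs. This stands as a view of the likely intent. A reader might infer that late ongoing AEs will be counted as 21-day events; the documents support only that they would be if 5.3.1.5 is followed. No text gives 4.4.1.2.4 precedence.

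A second defence is that 5.3.1.5 places missing-onset AEs by the visit collected, so a month-6 event would carry a late visit number and stay out. The wording does not clearly achieve this. SAP 4.4.1.2.3 uses the visit field to find the last vaccination, and 4.4.1.2.4 then treats the AE as occurring just after that vaccination and includes it in these tables.

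A reader might also infer that the rule would create a false cluster of early events. It would not: the onset display has its own Missing row, and misfiled events would appear there rather than under D01-D04 or D05-D08. They would still add to the 21-day totals.

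The consequences are limited in other ways too. The assumed 1% to 5% has no source in the documents. The tables count participants, so someone who already has a 21-day AE is not added again to the any-AE row. The SAP does not say that an ongoing AE has a blank stop date. Protocol 8.4.3 has investigators report a date of disappearance or of chronicity for some AEs, and whether that fills the stop-date field is not stated. Formulation selection used safety data only to D43, all analyses are descriptive, and SAP 5.1.2.4 says the formulation is not being taken further. SAEs, AESIs and MAAEs also have their own tables by period, so no event disappears from the report. All of this lowers the stakes; none of it reconciles the two sections.

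**Conclusion.** The contradiction is certain from the text: 5.3.1.5 makes onset depend on a date that 4.4.1.2.4 does not use. The misfiling is conditional. It requires that programming follows 5.3.1.5 and that ongoing AEs have a blank stop date. It can affect only SAEs, AESIs and MAAEs that start after day 22. The loss of onset category for earlier ongoing AEs, and of the derived onset for the non-study-vaccine cut, rests on the same two conditions.

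Any count is illustrative and an upper bound: at most about 4 to 22 of 440 participants at an assumed 1% to 5%. In groups of 10 or 20, one event would move a 21-day proportion from 0% to 10% or 5%. No hypothesis test or formal decision rule is touched. It is an error as written in the definition of a primary safety table, modest in effect and worth correcting.

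**What to change.** Replace the sentence in SAP 5.3.1.5 with one to this effect: *Time of onset is set to missing only when the AE start date or the date of the last vaccination is missing or incomplete; a missing or incomplete stop date affects duration only.* This agrees with 4.4.1.2.4 and 4.4.1.2.5, keeps the day-100 and day-300 examples out of the 21-day tables, and restores the onset needed for the non-study-vaccine cut.

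The cost is one SAP sentence and a check that the onset derivation in the safety programs uses only those two dates. No data collection or design feature changes. If outputs have already been produced under 5.3.1.5, rerun the 21-day unsolicited AE tables and the onset displays.
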